2.4.4.1.2 Descriptive analyses of Day 28 PCR-corrected ACPR

Frequency table for Day 28 PCR-corrected ACPR, ETF, LCF, LPF or on rescue before Day 7 without WHO criteria, including proportion, percentage and exact binomial 95% CIs (two-sided by using Clopper-Pearson method for calculating binomial CIs) by treatment arm, will also be provided using FREQ procedure in the PP and in the mITT population separately. The number of patients from the PP population and not evaluable for the PCR-corrected ACPR at Day 28 (i.e. patients with re-infection, or undetermined, negative or missing PCR) will be also detailed.

In addition a bar chart of the percentage of subjects meeting ACPR (with two-sided 95 CIs) will be presented.

2.4.4.1.3 Logistic regression on dose-response for Day 28 PCR-corrected ACPR

Dose-response in PCR-corrected ACPR will be done similarly to Day 28 crude-ACPR detailed in [Section 2.4.4.2.1.1](#).

2.4.4.2 Analyses of secondary efficacy endpoints

Apart from Day 28 crude ACPR, all other secondary efficacy endpoints will be reported and analysed on the mITT only.

2.4.4.2.1 Day 28 crude APCR

2.4.4.2.1.1 Logistic regression on dose-response

The dose-response association of single-dose OZ439/FQ for Day 28 crude-ACPR will be analyzed using a logistic regression with the probability of a response in Day 28 crude-ACPR and increasing dose of OZ439.

Baseline parasitemia (in \log_{10}) and age (in years) will be tested as covariates. If needed, some other covariates like sex, weight (in kg), country or site will be tested in the model. The selection of the best fitted model will be done by calculating the fit statistics like AIC, BIC among on all tested models, based on the choice of the predictor variables (separated AUC vs combined AUC). The best model detected with the fit statistic chosen by the statistician will be specified in a footnote of the summary table.

The Wald test will be used to test the OZ439 dose effect on Day 28 crude-ACPR.

This model will be run using SAS logistic procedure or similar using the outcome (response) binary variable (0/1) and the explicative variable dose susceptible to influence it.

Results of logistic regressions of Day 28 crude-ACPR on OZ439 dose level will be provided in a summary table including odds ratio estimates, the corresponding 95% Wald confidence intervals (CI) and p-value for each dose level and covariates.

Dose-response will be done with and without vomiters if relevant.

2.4.4.2.1.2 Descriptive analysis

Frequency table for Day 28 crude-ACPR, ETF, LCF, LPF or on rescue before Day 7 without WHO criteria, including proportion, percentage and exact binomial 95% CIs (two-sided by using Clopper-Pearson method for calculating binomial CIs) by treatment arm, will also be provided using FREQ procedure. The number of patients from the PP population and not evaluable for the PCR-corrected ACPR at Day 28 (i.e. patients with re-infection, or undetermined, negative or missing PCR) will be also detailed.

2.4.4.2.1.3 Logistic regression on exposure-response

Exposure-response in crude ACPR will be done similarly to Day 28 PCR-corrected ACPR detailed in [Section 2.4.4.2.1.1](#).

2.4.4.2.2 Parasitemia

Descriptive statistics (n, mean, geometric mean, standard deviation, median, Q1, Q3, minimum, and maximum) for parasitemia data (number of parasites/ μ L) (raw data and absolute change from baseline) will be displayed at baseline, and each post-baseline assessment.

Time profile plots (Mean \pm SEM) of parasitemia will be provided for each treatment arm, one curve per arm.

Box-Whisker plots over time of positive parasitemia levels will be provided by treatment arm.

Assessments performed after start of rescue treatment will not be included in above summaries

2.4.4.2.3 Observed Parasite reduction ratio

Descriptive statistics (such as arithmetic mean, geometric mean, standard deviation, median, Q1, Q3, minimum, and maximum) will be provided for each treatment arm.

Relationship between median blood concentrations for FQ (respectively blood concentrations for SSR97213 and plasma concentrations for OZ439) versus time-specific parasite reduction ratios (percent parasite reduction ratio [%PRR]) will be represented thanks to a scatter plot (one curve per treatment arm). Same analysis will be done for parasite clearance rate.

2.4.4.2.4 Parasite clearance rate and derived parameters

The parasite clearance rate, PC50, PC99 and estimated parasite reduction ratios (PRR24, PRR48 PRR72) will be summarized descriptively. However, data from patients with a poor fit to the linear model ($R^2 < 0.75$) will be excluded from the analysis.

2.4.4.2.5 Parasite clearance half-life (time to 50% parasite reduction) and time to 99% parasite reduction

Point estimate and 95% confidence interval for the geometric mean of T_{PC50} and T_{PC99} will be provided pooled across the 4 treatment group and separately for each dose group, using a linear fixed effect model.

Descriptive statistics (such as median, minimum, and maximum) will be provided for each treatment arm.

2.4.4.2.6 Time to parasite clearance

Time to parasite clearance will be analysed using two endpoints:

- Time to confirmed parasite clearance
- Time to parasite clearance (with or without confirmation)

Descriptive statistics (such as median, 25% and 75% percentiles, minimum, and maximum) for each endpoint will be provided for each treatment arm.

2.4.4.2.6.1 Kaplan-Meier method

The time to each parasite clearance endpoint will be estimated by the failure function, $F(t)=P(T \leq t)$, probability that a patient will have parasite clearance before or at time t , using Kaplan-Meier method. The Kaplan-Meier (product-limit) estimate of the failure function for each group will be plotted on a same graph.

Cumulative number of events i.e. parasite clearances - and censures, in addition to quartiles of the survival times with their 95% confidence interval will be provided by treatment arm, and overall. Percentage will be based on the number of patients included in the analysis.

The model will run by using the SAS LIFETEST or ICLIFETEST procedures in order to compute and plot the estimate of the distribution of the survival time.

At $t=$ Hour 24, Hour 48, Hour 72, the number of patients at risk just prior t , the number of events and censures, and the probability that the time to parasite clearance exceeds t , with its 95% confidence interval, will be provided by treatment arm, and overall.

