2.1.4.2.3 Parasite clearance time (PCT)

For a conservative approach, parasite clearance should not be claimed based on negative parasitemia obtained by imputation. Therefore, in this section **no imputation of missing parasitemia** will be used, except in case of concomitant fever where the missing parasitemia will be considered as positive.

Timing to consider

In this section, except otherwise specified, the post-dose timing associated to a parasitemia will refer to:

- its assigned time point as defined in [Section 2.5.4.1](#), if it exists,
- its actual post-dose timing as defined in [Section 2.5.4](#) and expressed in hours, if outside defined time windows. None or very few are expected, otherwise it should be taken into account in the analyses.

Establishing the clearance

A blood thick film is considered negative when asexual forms of *P. falciparum* are reported as absent on the dedicated e-CRF page, even if other species are reported.

The parasite clearance will be concluded as soon as two consecutive thick films are negative, with second film prepared within 6 to 12 hours of the first (actual times). In case, the second film has been performed less than 6 hours or greater than 12 hours of the first, then the parasite clearance will be confirmed or invalidated by the thick film following the second one, whatever the timing of this third film:

- If this third film is negative, then the clearance is confirmed.
- If this third film is positive, then the clearance is invalidated.

Time to parasite clearance

When the parasite clearance is confirmed, the time to parasite clearance is the post-dose timing associated to the first negative thick film, as defined above.

In case the parasite clearance is not observed or confirmed before withdrawn (for any reason) or before start of rescue therapy, then the time to parasite clearance will be censored at the time of the last blood film (using the post-dose timing above defined) before withdrawn or rescue therapy start, whichever comes first. Blood films (including date and time of recording) performed the day of rescue start are regarded as before rescue.

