2.1.4.2.8 Fever clearance time (FCT)

FCT is the time from start of study drug administration until temperature remained below 37.5°C.

Fever is defined by a body temperature $\geq 37.5^{\circ}\text{C}$ for axillary temperature or by a body temperature $\geq 38^{\circ}\text{C}$ for other routes of measurement.

Timing to consider rules will be similar to what it is described in [Section 2.1.4.2.3](#). The FCT is the post-dose timing associated to the first vital sign assessment as defined above.

In case the FCT is not observed or confirmed before withdrawn (for any reason) or before start of rescue therapy, then the FCT will be censored at the time of the last vital sign assessment (using the post-dose timing above defined) before withdrawn or rescue therapy start, whichever comes first.

FCT is not applicable for patients with baseline body temperature $< 37.5^{\circ}\text{C}$ for axillary temperature (or $< 38^{\circ}\text{C}$ for other routes of measurement) or missing.

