2.4.4.2.11 Time to fever clearance

Same analyses than those described in [Section 2.4.4.2.6](#) for time to parasite clearance.

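### Censoring at rescue makes the Kaplan-Meier probability of parasite (and fever) clearance too high when some patients are rescued uncleared and others clear later

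*SAP*

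**What the plan says.** SAP 2.1.4.2.3 covers patients who leave the study or start rescue without a confirmed clearance. For them, "the time to parasite clearance will be censored at the time of the last blood film". The earlier of the two exits sets the cut-off, and rescue given for treatment failure is not excepted. Films "performed the day of rescue start are regarded as before rescue", so a patient rescued on Day 3 is censored at the 72 h film.

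SAP 2.1.4.2.8 does the same for fever: "the FCT will be censored at the time of the last vital sign assessment". It applies only to patients febrile at baseline.

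SAP 2.4.4.2.6.1 defines the reported quantity F(t) as the "probability that a patient will have parasite clearance before or at time t , using Kaplan-Meier method". It is plotted by arm and tabulated at 24, 48 and 72 h, with quartiles and with counts of events and censorings. SAP 2.4.4.2.11 analyses fever clearance with the methods described "for time to parasite clearance".

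Protocol 7.7.1 allows rescue once there is evidence of treatment failure. The early criteria include a Day 2 count above Day 0, a Day 3 count of at least 25% of Day 0, and Day 3 parasitemia with fever. Any parasitemia from Day 7 is a failure. Neither document plans a competing-risk estimate for clearance.

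**The concern.** Kaplan-Meier censoring assumes that a censored patient would have gone on to clear at the same rate as those still at risk. A patient rescued for failure is selected because the parasites are not clearing, and after rescue, clearance by study drug can no longer be observed. Protocol 9.1.1.3 describes the two exits itself: films continue until the patient clears or meets the rescue criteria. Treating the second exit as censoring gives an estimate for a hypothetical setting without rescue, while the SAP labels it as the probability that a patient clears.

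The SAP handles the same patient differently elsewhere. In 2.1.4.2.4 a patient who never clears gets a re-emergence time of zero, and rescue after clearance counts as an event unless it is a protocol violation or for another species.

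Clearance time is a named secondary endpoint for the OZ439 dose-response. If uncleared rescues were more frequent in one arm, that arm's curve would be raised most and the contrast between arms would shrink.

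**Working it through.** **Inputs.** Arm size: 30 evaluable (protocol 10.1). The plan's own arithmetic holds approximately: 30/0.85 = 35.3 against a stated 35 per arm. No figure is stated for the clearance analysis, so clearance and rescue rates are assumed. Non-failing patients clear 20% at 24 h, 30% at 36 h, 20% at 48 h, 20% at 72 h and the rest at 96 h, rounded to whole patients. Rescued patients are uncleared.

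**Estimators.** 1-KM is one minus the product of (1 - cleared/at risk), with rescued patients leaving as censored after their last film. The cumulative incidence (CIF, Aalen-Johansen) treats rescue as a competing event. With no other censoring it equals cleared/30.

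**3 of 30 rescued on Day 2.** The other 27 clear as 5, 8, 5, 5 and 4.
- After the 48 h film, 12/30 are uncleared. Three are censored and 9 remain at risk; 5 of these clear at 72 h.
- 1-KM = 1 - (12/30)(4/9) = 82.2%. CIF = 23/30 = 76.7%.

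**6 of 30 rescued on Day 2.** The other 24 clear as 5, 7, 5, 5 and 2.
- After 48 h, 13/30 are uncleared. Six are censored and 7 remain; 5 clear at 72 h.
- 1-KM = 1 - (13/30)(2/7) = 87.6%. CIF = 22/30 = 73.3%.

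**6 of 30 rescued on Day 3.** All 13 uncleared patients are still at risk at the 72 h film and 5 clear. 1-KM = 1 - 8/30 = 73.3% = CIF.

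| Rescued uncleared | 48 h: 1-KM / CIF | 72 h: 1-KM / CIF | 96 h: 1-KM / CIF |
|---|---|---|---|
| none | 70.0 / 70.0 | 90.0 / 90.0 | 100 / 100 |
| 3 on Day 2 | 60.0 / 60.0 | 82.2 / 76.7 | 100 / 90 |
| 6 on Day 2 | 56.7 / 56.7 | 87.6 / 73.3 | 100 / 80 |
| 3 on Day 2, 3 on Day 3 | 56.7 / 56.7 | 78.3 / 73.3 | 100 / 80 |
| 6 on Day 3 | 56.7 / 56.7 | 73.3 / 73.3 | 100 / 80 |
| 3 on Day 1, 3 on Day 2 | 62.1 / 56.7 | 89.2 / 73.3 | 100 / 80 |

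The 24 h values agree in every row, and so do the medians. The 75% point can move: with 6 Day 2 rescues it is 72 h by 1-KM and 96 h by CIF.

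**General form for Day 2 rescues.** Let u be the share uncleared at 48 h (rescued included), x the share rescued then, and c the share clearing between 48 and 72 h. The excess at 72 h is c·x/(u - x). For 3/30 this is (5/30)(3/9) = 5.6 points; for 6/30 it is (5/30)(6/7) = 14.3 points. Simple binomial standard errors are √(0.767 × 0.233/30) = 7.7 points and √(0.733 × 0.267/30) = 8.1 points. The excess is zero when nobody clears later.

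**Second assumed profile.** Clearance is lognormal with log-SD 0.45, and 3 of 30 are rescued at 48 h.
- Median 36 h: the shares cleared by 48 and 72 h are 0.739 and 0.938, so u = 0.335, c = 0.179 and the excess is 0.179 × 0.1/0.235 = 7.6 points.
- Median 48 h: the shares are 0.500 and 0.816, so the excess is 0.284 × 0.1/0.45 = 6.3 points.
- Simulated arms of 30 with a 24 h median give 7.3 points.
- With 2 of 30 rescued, simulation gives 4.9, 5.1 and 4.2 points at medians of 24, 36 and 48 h.

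**The case against.** The strongest reply is that the effect is narrow and partly visible already. Much of that stands.

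- **Two of the early-failure criteria listed above do no harm at the tabulated times.** Both Day 3 criteria are judged at the 72 h film, where the patient still counts as at risk. Only rescues on Day 1-2 move the 72 h value.
- **The curve need not reach 100%.** If everyone else has cleared by 72 h and 6 patients are censored there, 1-KM stays at 24/30 = 80%, the same as CIF. The 100% at 96 h in the table depends on some non-failing patients clearing that late.
- **A reader might infer that arms with more early failures will look as good as the others.** The figures do not support that in general. Against 90.0% in a failure-free arm, the 72 h values in the table run from 73.3% to 89.2%. Only the rows with six rescues by Day 2 come close.
- **A reader might also take the 28% expected failure with FQ alone (100% - 72%) as a guide to early rescue in that arm.** It is Day 28 PCR-corrected failure and includes recrudescence after clearance, so it fixes neither the number nor the timing.
- **The plan shows the raw material.** Events, censorings and numbers at risk are tabulated by arm, and early treatment failure is reported separately (SAP 2.4.4.1.2 and 2.4.4.2.1.2).
- **A Cox model that censors at rescue is legitimate.** It estimates a cause-specific hazard ratio.
- **For fever the link is less direct.** Fever alone does not trigger rescue. Parasitemia with fever on Day 3 does, so the censoring is still informative.

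These points limit the size and reach. They do not make 1-KM the probability that the SAP says it is.

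**Conclusion.** The point holds in this limited form. Once patients are rescued uncleared and others clear later, the planned estimate overstates the probability of clearance. Under the main assumed profile, 3 and 6 Day 2 rescues in 30 overstate it at 72 h by 5.6 and 14.3 points. Day 3 rescues give no difference at 24 to 72 h, and medians are unchanged throughout. These sizes rest on assumed clearance profiles and rescue counts, because the documents supply neither; with no rescues before 72 h the tabulated values are correct. Fever clearance follows the same rule, but its size was not calculated. The endpoints are secondary and descriptive, so the primary exposure-response test and the sample size are untouched. The documents do not establish that the bias falls mainly on FQ alone; that remains a possibility.

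**What to change.** In SAP 2.4.4.2.6.1, and through it 2.4.4.2.11:

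- Estimate F(t) by the Aalen-Johansen cumulative incidence function, with rescue before clearance as a competing event. Report it by arm at 24, 48 and 72 h and to the end of the curve.
- Keep censoring for withdrawal and loss to follow-up, and amend 2.1.4.2.3 and 2.1.4.2.8 to match.
- If a rescue-censored Kaplan-Meier curve is kept, label it as hypothetical: clearance had rescue not removed these patients.
- If the Cox model in protocol Table 8 and the SAP Appendix B summary table is run, describe its hazard ratio as cause-specific.

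The cost is SAP wording and one procedure option, using data already collected. The downside is that the reported clearance probability will be slightly less favourable where early failures occur.

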2.4.4.2.7 Time to re-emergence

Incidence of re-emergences will be summarized among patients with complete clearance (i.e those who initially responded). The survival distribution function of the time to re-emergence will be estimated using Kaplan- Meier method. The estimate of the survivor function for each group will be plotted on a same graph. Cumulative number of events (i.e. re-emergence) and censures, in addition to quartiles of the survival times with their 95% confidence interval will be provided by treatment arm. At times $t=$ Day 7, Day 14, Day 21 and Day 28, the number of patients at risk just prior t , the cumulated number of events and censures at t , and the probability that the time to reemergence exceeds t , with its pointwise 95% confidence interval, will be provided.

2.4.4.2.8 Time to recrudescence

Same analyses than those described in [Section 2.4.4.2.7](#) for time to re-emergence.

2.4.4.2.9 Time to reinfection

Same analyses than those described in [Section 2.4.4.2.7](#) for time to re-emergence.

2.4.4.2.10 Elapsed time below LOQ of parasitemia

Same analyses than those described in [Section 2.4.4.2.7](#) for time to re-emergence. All subjects within the associated population will be included.

2.4.4.2.11 Time to fever clearance

Same analyses than those described in [Section 2.4.4.2.6](#) for time to parasite clearance.

2.4.4.3 Multiplicity issues

No adjustment for multiplicity of comparisons was applied for primary or for secondary analyses.

2.4.4.4 Additional efficacy analyses

Additional efficacy analyses will be reported and analysed in the mITT population.

- Disease characteristics post-baseline

Descriptive statistic of the number (%) of patients experiencing clinical signs or symptoms related to malaria will be provided at each visit and for each sign or symptom, regardless of the presence of the sign/symptom at baseline, and within the subset of patients who the sign/symptom at baseline.

- Time to gametocytes clearance (blood smears)

Time to gametocytes clearance will be analyzed using Kaplan-Meier estimators. An overall overview including number of events and cumulative incidence of events with 95% CI will be provided in a summary table, survival curves will be plotted.

- Time to appearance of gametocytes (blood smears)

The first appearance of gametocytes will be presented by time after enrollment for all patients, by treatment arm. The denominator for computation of percentages is the mITT population within each treatment arm. Besides, time to gametocytes clearance will be analyzed using Kaplan-Meier estimators in the same way than time to gametocytes clearance.

- Time to gametocytes clearance (RT-qPCR)

Time to gametocytes clearance will be analyzed using Kaplan-Meier estimators. An overall overview including number of events and cumulative incidence of events with 95% CI will be provided in a summary table, survival curves will be plotted.

- Time to appearance of gametocytes (RT-qPCR)

The first appearance of gametocytes will be presented by time after enrollment for all patients, by treatment arm. The denominator for computation of percentages is the mITT population within each treatment arm. Besides, time to gametocytes clearance will be analyzed using Kaplan-Meier estimators in the same way than time to gametocytes clearance

2.4.5 Analyses of safety data

The summary of safety results will be presented by actual treatment group.

General common rules

All safety analyses will be performed on the safety population as defined in Section 2.3.3, unless otherwise specified, using the following common rules:

- Safety data in patients who do not belong to the safety population (eg, exposed but not randomized) will be listed separately.
- The potentially clinically significant abnormality (PCSA) values are defined as abnormal values considered medically important by the Sponsor according to predefined criteria/thresholds based on literature review and defined by the Sponsor for clinical laboratory tests, vital signs, and ECG.
- PCSA definitions (version dated May 2014) depending on the age, race, or sex of the patient are detailed separately in [Appendix A]. Specific PCSA criteria for children will use children's age at time of laboratory, vital signs and ECG assessments. Age will be collected in the eCRF by the clinical site.
- PCSA criteria will determine which patients had at least 1 PCSA during the on-treatment period, taking into account all evaluations performed during the on-treatment period, including nonscheduled or repeated evaluations. The number of all such patients will be the numerator for the on-treatment PCSA percentage.
- The treatment-emergent PCSA denominator by group for a given parameter will be based on the number of patients assessed for that given parameter in the on-treatment period by treatment group on the safety population.
- For quantitative safety parameters based on local laboratory/reading measurements, descriptive statistics will be used to summarize results and change from baseline values by visit and treatment group. Summaries will include the endpoint value and/or the worst on-treatment value. The endpoint value is commonly defined as the value collected at the same day/time of the last administration of IMP. If this value is missing, this endpoint value will be the closest value prior to the last dose intake. The worst value is defined as the nadir and /or the peak on-treatment post-baseline according to the direction (minimum or maximum) of the abnormality as defined in the PCSA list.
- Analyses of the safety variables will be essentially descriptive and no systematic testing between treatment groups is planned.

